7. RESEARCH PROCEDURES

General Procedures. Subjects who meet the inclusion criteria will reside on the Clinical Research Unit (CRU) at the University of Kentucky Medical Center while they participate. During their participation in the research protocol, subjects will not be allowed to leave the CRU unattended, nor will visitors be allowed. After completing the protocol, all subjects will be debriefed and offered a referral to a drug use treatment program. Subjects will be enrolled for approximately one month. Experimental sessions and dosing will be conducted as shown in Table 1. After three days of maintenance on each zolmitriptan dose (i.e., double the time necessary to achieve steady state concentrations as outlined below; Dixon et al., 1997), the reinforcing and subjective effects of intravenous cocaine (0, 10, and 30 mg/70 kg), as well as a range of impulsive behaviors, will be measured across three experimental sessions. Note, the maximum intravenous cocaine dose will be 40 mg regardless of weight, but we will continue to refer to this dose condition at 30 mg/70 kg throughout the protocol. Following completion of the Practice Session, a nurse from the UKHealthCare Vascular Access Team (VAT) will insert a needle into the subject's arm. The needle will be removed and a long intravenous midline catheter (approximately 3 – 5 inches) will stay in the vein near the subject's armpit. The placement of this midline catheter will allow for longer-term intravenous access (e.g., 30 days) to receive fluids (i.e., saline) and cocaine than a typical venous catheter that would be placed prior to experimental sessions. This eliminates the need to re-insert short-term catheters for IV access (e.g., 2 – 3 days). The removal of the midline catheter will occur upon completion of the last experimental session or when deemed necessary by the study physicians and/or hospital policy. Peripheral intravenous catheter may be inserted in the subject's arm if the midline catheter needs to be removed or if an unforeseen event obstructs administration of cocaine (e.g., leaking).

Table 1.

Day	Details
0	Admission to the CRU. Practice Session wherein subjects will be familiarized with the experimental session tasks.
1	Medical Safety Session. Subjects will receive the cocaine doses to be tested in this study (0, 10 and 30 mg/70 kg) separated by 60 minutes.
2-7	Placebo maintenance. Placebo administered twice daily (0700 and 1900 hours).

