5-7	Experimental Sessions 1-3. Subjects complete 1 sample and 5 choice trials to receive cocaine (0, 10 and 30 mg/70 kg) or money (\$6.00) by responding on the concurrent progressive-ratio schedule. Assessment battery completed following administration of the sampling dose as described below.
8-9	Washout. Placebo administered twice daily (0700 and 1900 hours).
10-15	Zolmitriptan (2.5 mg/day) maintenance. Administered in divided doses (0700 and 1900 hours).
13-15	Experimental Sessions 4-6. Details are the same as for days 5-7.
16-17	Washout. Placebo administered twice daily (0700 and 1900 hours).
18-23	Zolmitriptan (5 mg/day) maintenance. Administered in divided doses (0700 and 1900 hours).
21-23	Experimental Sessions 7-9. Details are the same as for days 5-7.
24-25	Washout. Placebo administered twice daily (0700 and 1900 hours).
26-31	Zolmitriptan (10 mg/day) maintenance. Administered in divided doses (0700 and 1900 hours).
29-31	Experimental Sessions 10-12. Details are the same as for days 5-7.
32	Discharge.
Note	Dosing order is illustrative. All doses will be administered in random order.

This experiment will require each subject to participate for approximately one month. Experimental sessions will be conducted as outlined in Table 1 above. We would like to note four important points relating to the table above: 1) To avoid experimental testing on weekends, subjects may be maintained on zolmitriptan or placebo for longer than outlined above (i.e., maintenance conditions may last for two days longer than in the example above). 2) The order of zolmitriptan maintenance conditions and cocaine experimental sessions will be randomized. 3) All maintenance conditions will be followed by a two-day washout period in which the participant receives a placebo delivered in a double-blinded fashion. 4) If subjects leave the protocol for a reason unrelated to study procedures (e.g., a family emergency or dental problems), they may be re-admitted

with physician approval to complete the remainder of the protocol, picking up in the condition where they left off (i.e., sessions/dose conditions that have already been completed will not be repeated). Thus, they may not complete the protocol over one approximately 33-day admission but can complete the protocol over two admissions totaling approximately 33 days.

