Cardiovascular Measures and Body Temperature. Heart rate, blood pressure, cardiac rhythmicity (i.e., electrocardiograms [ECG]) and body temperature will be recorded before cocaine administration and at frequent intervals after dose administration. Cardiac rhythmicity (i.e., electrocardiograms [ECG]) will be recorded for 30 minutes before intravenous cocaine administration and continuously during each experimental session. No drugs will be administered if a subject's heart rate is \geq 90 bpm if systolic pressure \geq 140 or diastolic pressure \geq 90 mmHg. A subject will be excluded from further participation if at any time he or she exceeds our cardiovascular safety and tolerability thresholds (i.e., heart rate above 130 bpm, diastolic pressure increases above 120 mmHg or systolic pressure above 180 mmHg or clinically significant ECG changes) after administration of zolmitriptan alone, cocaine alone or cocaine-zolmitriptan combinations. Heart rhythmicity will be assessed via 3-lead telemetry continuously during each experimental session, will be printed out and verified as normal prior to dose administration, and will be monitored continuously for a minimum of 15 minutes following each infusion.

Safety and tolerability outcomes: Udvalg for Kliniske Undersøgelser (UKU). The UKU is a standardized, validated rating scale that assesses over 50 potential side effects (e.g., sedation, akathisia, weight change) associated with administration of centrally acting drugs (Lingjaerde et al., 1987). It also includes a global assessment of how these side effects interfere with functioning. This questionnaire will be completed daily at 1630 h. We have routinely used this scale to evaluate the safety and tolerability of maintenance doses and cocaine ([name] et al., 2008; [name] et al., 2009; [name] et al., 2007; 2008; 2016). A subject will be excluded from further participation if at any time he or she exceeds adverse event safety and tolerability thresholds (i.e., an effect rated as severe lasting more than 24 h) after drug administration.

Drug Dose and Administration. All drugs will be administered under double-blind conditions and medical supervision in randomized order. We currently hold an IND for intravenous cocaine administration and will modify it to test intravenous cocaine during zolmitriptan maintenance. To maintain the blind, only [name] and the Investigational Drug Service will have access to dose conditions for subjects.

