Physiological data. Three sets of analyses will be conducted on the cardiovascular outcomes and body temperature data. First, data will be analyzed as peak effect using two-factor repeated-measures ANOVA. Cocaine (0, 10, and 30 mg/70 kg) and zolmitriptan (0, 2.5, 5, and 10 mg/day) will be factors for these analyses. A significant augmentation or attenuation of the effects of cocaine will be inferred if the main effect of the zolmitriptan or the cocaine-zolmitriptan interaction attains statistical significance in the ANOVA. If the cocaine-zolmitriptan interaction attains statistical significance, the MSE term will be used to conduct Tukey's HSD *post-hoc* test to make appropriate pair-wise comparisons between means. Second, AUC will be calculated for each subject using the trapezoidal method and analyzed in the same fashion as peak-effect data. Third, these data will be analyzed by repeated-measure ANOVA with cocaine, zolmitriptan and time as factors. The MSE term for the cocaine-zolmitriptan-time interaction will then be used to make appropriate pair-wise comparisons.

Safety and tolerability data. For items from the UKU, which will have one data point per day, data will be analyzed using a two-factor repeated-measures ANOVA. Zolmitriptan (0, 2.5, 5, and 10 mg/day) and day will be factors for these analyses. The MSE term for the zolmitriptan-day interaction will then be used to make appropriate pair-wise comparisons.

Evaluating Relevant Biological Variables. We will conduct exploratory analyses to evaluate potential effects of relevant biological variables. Specifically, we will repeat the analyses described above including factors like sex, age, race, and other drug use to determine whether and how these variables might influence study outcomes. Although exploratory, these outcomes can inform future grant applications in terms of how individual differences influence responses to 5-HT_{1b} activation in people with cocaine use disorder.

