9. POTENTIAL RISKS

The behavioral and physiological assessment procedures employed in this study are benign. The risks to the study subjects are those related to the administration of the drugs under study. Cocaine has safely been administered to human subjects under controlled-laboratory conditions. The relative safety, as well as the contraindications and possible side effects of cocaine and zolmitriptan are well known and documented. However, the administration of any drug involves some risks simply because individuals differ in their reactions

to drugs. The main risk is that subjects will experience side effects that may be unpleasant. The side effects of zolmitriptan and cocaine may change as a function of the drug combinations, which is why we will not be dosing more than the recommended daily amount of zolmitriptan (i.e., 10 mg/day) in this study.

Common side effects of zolmitriptan include dry mouth, nausea, pain/pressure in neck or throat, drowsiness, weakness, warmth, redness or mild tingling under the skin, increased heart rate and increased blood pressure. More serious side effects include chest pain, sudden lateral numbness or weakness, sudden headache, confusion, problems with vision, speech or balance, dizziness, severe stomach pain, hematochezia, serotonin syndrome and cyanosis.

Common side effects of cocaine include anxiety, restlessness, diuresis, irritability, suppressed appetite, insomnia, gastrointestinal upset, increased heart rate, increased blood pressure, palpitations, and arrhythmias. More serious side effects following the chronic, unsupervised administration of much higher doses of cocaine have occurred and include psychotic episodes, suppressed breathing, seizures, myocardial infarctions, heart failure and death.

The doses to be administered in the present experiment were chosen to minimize, if not eliminate, the chance of these side effects occurring since these side effects are related to dose. Thus, it is unlikely that subjects will experience side effects during the experimental protocol. All experiments proposed in this application will be conducted at the CRU and under medical supervision. Side effects of the drugs are temporary, usually dissipating in less than 24 hours.

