17. DATA AND SAFETY MONITORING

Data Monitoring Plan

Data will be collected using a computerized data collection and management system wherever possible. This system automates the collection of data, which ensures the accuracy and completeness of data collection. The data are stored in a unique file on the hard drive of the computer and are printed after all the tasks are completed. In all instances, the data files do not contain the name of the subject, but instead, a unique four-digit number identifies each subject. A computer file linking the unique number with the subject's name will be kept on a stand-alone, password-protected computer. All data requiring hand entry (e.g., cardiovascular measures) will be double entered by two separate staff members and comparison macros run to ensure accuracy. Data files for experimental tasks and physiological measures from each experimental session will be manipulated and combined into a single electronic spreadsheet for each subject by the PI. Data for all subjects will then be combined into a single electronic spreadsheet and separated by experimental measure for statistical analysis.

The primary outcomes will be the break points for drug and money in the cocaine self-administration task, analyzed as a function of zolmitriptan maintenance conditions. Secondary outcome measures will be abuse-related subjective and cognitive effects of cocaine, analyzed as a function of zolmitriptan maintenance conditions. Tertiary outcome measures will be the physiological and side-effects of cocaine, analyzed as a function of zolmitriptan maintenance conditions. Data will be analyzed using repeated measure ANOVA. The alpha level will be set at 5%.

As noted above, wherever possible, data are collected using an automated computer system, which increases the accuracy and completeness of data collection and ensures the validity and integrity of the data. The initial data manipulation described above will be conducted twice and compared. The quality of manipulated data and data analyses will be monitored by random inspection by the PI and/or Co-Investigators.

Safety Monitoring Plan

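### The planned UKU side-effect model leaves cocaine out, so it cannot estimate UKU side effects by cocaine dose or a cocaine-zolmitriptan interaction

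*Combined protocol and SAP*

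**What the plan says.** Section 7 (Safety and tolerability outcomes) introduces the UKU, a scale of over 50 potential side effects, and fixes its timing: "This questionnaire will be completed daily at 1630 h". The same paragraph says the group has routinely used the scale to "evaluate the safety and tolerability of maintenance doses and cocaine".

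Section 7 (Data Analysis, Safety and tolerability data) specifies a two-factor repeated-measures ANOVA for each UKU item: "Zolmitriptan (0, 2.5, 5, and 10 mg/day) and day will be factors for these analyses". It continues: "The MSE term for the zolmitriptan-day interaction will then be used to make appropriate pair-wise comparisons".

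Section 17 (Data Monitoring Plan) sets the outcome: "Tertiary outcome measures will be the physiological and side-effects of cocaine, analyzed as a function of zolmitriptan maintenance conditions". Section 9 adds: "The side effects of zolmitriptan and cocaine may change as a function of the drug combinations".

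On the schedule, sessions begin "After three days of maintenance on each zolmitriptan dose" and occupy three days, one for each cocaine dose (0, 10 and 30 mg/70 kg). The notes under Table 1 say that the order of the cocaine sessions is randomized and that, to avoid weekend testing, "maintenance conditions may last for two days longer than in the example above".

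**The concern.** Break points, subjective ratings, impulsivity tasks and physiological measures are all analysed with cocaine and zolmitriptan as factors. The UKU is the only outcome family analysed without cocaine, although its session-day rating follows that day's sampling dose (1000 h) and all five choice trials (1100 to 1500 h).

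A zolmitriptan x day model can separate session days from cocaine-free days, but not 30 mg/70 kg from saline. An effect specific to the combination is averaged with saline and cocaine-free days, and differences between cocaine doses go into the error term. At stake is what the trial can report from its broadest side-effect scale about tolerability of the combination. The plan also does not say which days make up the day factor when a block is extended.

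**Working it through.** **Inputs from the document.** 20 completers; 4 zolmitriptan levels; 3 cocaine levels; a six-day block (3 cocaine-free days, then 3 session days), up to 8 days if extended; random cocaine order; one UKU rating a day; alpha 0.05.

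**The plan's own power figure.** The only one is f = 0.27 at 80% power with 20 completers. For a four-level within-subject factor, assuming sphericity and a correlation of 0.5 (neither is stated), lambda = f² x N x m / (1 - rho) = 0.27² x 20 x 4 / 0.5 = 11.7 on 3 and 57 df. Power is 0.799, so the figure reproduces. It gives no information on the UKU.

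**Dilution.** Suppose 10 mg/day adds d to a UKU item on the 30 mg/70 kg day and g x d on the 10 mg/70 kg day, and nothing otherwise. With random order, each session-day cell contains each cocaine dose in one third of subjects on average. For a block of D days:

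- expected shift in the zolmitriptan main effect = d(1 + g)/D
- expected shift in a session-day cell = d(1 + g)/3

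| Shape of effect | Main effect, D = 6 | Main effect, D = 8 | Session-day cell |
|---|---|---|---|
| 30 mg/70 kg only (g = 0) | 1/6 (six-fold) | 1/8 (eight-fold) | 1/3 (three-fold) |
| Half as large at 10 mg/70 kg (g = 0.5) | 1/4 (four-fold) | 3/16 (5.3-fold) | 1/2 (two-fold) |
| Equal at both doses (g = 1) | 1/3 (three-fold) | 1/4 (four-fold) | 2/3 (1.5-fold) |

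The D = 8 column applies only if every day of an extended block is used. These factors describe the mean difference. Averaging six days also reduces within-subject noise by √6 = 2.45. Against a single-day comparison, the worst-case loss in signal-to-noise over six days is therefore 6/2.45, about 2.4-fold.

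**Power by simulation.** Assumptions: 20 subjects, 4 x 6 days, independent normal residuals with SD 1, and cocaine's own effect 0.5 SD at 10 mg/70 kg and 1.0 SD at 30 mg/70 kg. The extra effect sits only in the 10 mg/day plus 30 mg/70 kg cell.

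| Extra effect | Planned: zolmitriptan | Planned: zolmitriptan x day | Session days: cocaine x zolmitriptan |
|---|---|---|---|
| 1.0 residual SD | about 22% | about 10% | about 63% |
| 1.5 residual SD | about 45% | 18-19% | 95-96% |

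Independent runs agree within simulation error (22%, 10-11% and 61-63% in the first row). As a cross-check, scaling by total SD with a correlation of 0.5 makes 1.0 SD equal to 1/√0.5 = 1.41 residual SD, and gives 41%, 20% and 93%.

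**Other shapes and contrasts.** With the extra effect half as large at 10 mg/70 kg, planned main-effect power is about 44%; with it equal at both doses, about 72%. In the 1 SD case, the single comparison of 10 with 0 mg/day at 30 mg/70 kg has about 85% power as an uncorrected paired test, but about 43% under Tukey's HSD over 12 cells. For a plain zolmitriptan side effect of 0.5 SD on all days at 10 mg/day, the six-day planned model has about 98% power and session days alone about 79%.

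**The case against.** Four readings are tempting and go too far.

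*The tertiary question cannot be answered at all.* The document does not support this. The physiological half of that outcome has cocaine as a factor. Many ARS and DEQ items (nausea, dizziness, shakiness, nervousness, irregular or racing heartbeat, bad effects) are side effects in substance, and Aim 2 analyses the subjective data by cocaine and zolmitriptan. Section 17 (Safety Monitoring Plan) lists subjective measures among the ways of monitoring adverse events, and individual exclusion thresholds and weekly adverse-event review operate as well. The Section 9 sentence on combinations justifies the zolmitriptan dose cap; it does not assign that question to the UKU.

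*Combination effects are diluted six-fold in general.* Six-fold needs the main effect, exactly six days and an effect at one cocaine dose only. The plan takes its pair-wise comparisons from the zolmitriptan-day error term, and in session-day cells the dilution is three-fold at most.

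*The planned model is nearly blind to the combination.* That depends on the shape of the effect: 22% becomes 44% or 72% if 10 mg/70 kg contributes.

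*The right analysis would have 85% power.* That is an unadjusted test on the one cell where the effect was placed. The fair comparator is the interaction test, about 63%.

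Two practical objections also stand. Session days alone lose power for zolmitriptan's own side effects. And a 1630 h rating reflects 1 to 6 infusions, up to five of them chosen by the subject, while the study's hypothesis is that zolmitriptan reduces that choice.

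None of this supplies the missing factor. The ARS and DEQ are rated around the sampling dose only; the UKU covers over 50 effects after all the day's infusions.

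**Conclusion.** The concern holds for the UKU alone. As written, its model cannot estimate side effects by cocaine dose or a cocaine-zolmitriptan interaction, and this does not match the Section 17 outcome or the use of the scale described in Section 7. That conclusion follows from the stated factors and the random cocaine order, and needs no simulation.

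The size depends on assumptions. Dilution runs from 1.5-fold to eight-fold over the shapes and block lengths considered: six-fold in the main effect and three-fold in session-day cells for an effect at 30 mg/70 kg only, in a six-day block. The powers rest on normal, independent residuals and assumed effect sizes. UKU items are ordinal, so only the ranking of the analyses should be relied on. This is a tertiary outcome, and the correction is worth making before unblinding so that it is not post hoc.

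**What to change.** Add to Section 7 (Safety and tolerability data) a cocaine (3) x zolmitriptan (4) repeated-measures analysis of the 12 session-day UKU ratings, parallel to the physiological data. Keep the zolmitriptan x day model for zolmitriptan's own side effects, since replacing it would lose power there. State that its day factor covers the six standard days of each block, and summarise extra weekend days descriptively.

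Report the number of infusions received per session alongside the new table, descriptively only. Infusions received are a post-randomization outcome that zolmitriptan may change, so they should not be used to stratify or as a causal adjustment. State that the session-day result reflects total cocaine received that day, not the sampling dose alone.

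Cost: analysis wording and one more table. The ratings and each day's cocaine dose are already collected, so no visits, subjects or measurements are added. The limit in interpretation from self-administered exposure remains.

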8. RESOURCES

This study will take place at the CRU. Study sessions will only be conducted on weekdays. All drug administration will take place at the UK CRU in a room equipped with all the necessary physiologic and computer equipment for the study. [name] is an adult psychiatrist who has worked extensively with individuals with substance use disorders in both the clinical and research setting, and he is the responsible medical investigator for this study. [name] is an Associate Professor in the departments of Anesthesiology and Surgery, Chief in the Division of Critical Care Medicine and Medical Director of the UK Healthcare Neurocritical Care Service and has worked on previous intravenous cocaine protocols conducted in our laboratory. [name] is a psychiatrist who has worked extensively with individuals with substance use disorders in both the clinical and research setting, and he is the back-up medical investigator for this study. They will be available to attend to medical problems as well as any psychological or psychiatric issues that may arise. Drs. [name], [name], and [name] will provide scientific oversight for the study and have safely completed numerous human behavioral pharmacology studies. Overall, the study team and resources described above are well equipped to protect subjects and successfully implement, carry out and complete this study protocol.

